### **Abstract**

Obtaining reliable vascular access is “one of the most basic yet critical components of patient care both in hospital and ambulatory patient settings”. Over one billion peripheral intravenous catheters (PIVCs) are placed annually worldwide, with nearly 300 million annually in the United States; this does not take into account additional vascular catheters such as central venous catheters and arterial catheters. Given that incidence it is concerning that still, first-attempt success incidence varies between 18-79%; illustrating a 21-82% first-attempt failure rate. The use of ultrasound guidance in vascular access procedures has gained significant traction by both medical and nursing staff in inpatient and outpatient settings. Standard ultrasound training for vascular access utilizes a cross-sectional viewing plane; however, the use of a longitudinal viewing plane is also beneficial. Utilization of both planes is challenging by the end-user due to mechanical manipulation (rotation of probe) that must be done intra-procedure. The goal of this protocol is to evaluate the rate of cannulation success and efficiency of a dual-plane ultrasound probe (Butterfly iQ+; Butterfly Network, Inc.; FDA approved) in ultrasound-guided vascular access procedures as compared to a standard single-view ultrasound probe in the operating room setting during placement of arterial catheters.

### **Research Plan**

#### **I. Specific Aims**

Utilization of ultrasound guidance for vascular access procedures is commonplace in inpatient and outpatient care settings, specifically procedural and critical care settings. Standard ultrasound probes offer the operator a single-plane view, necessitating rotation of probe to attain dual views which are complimentary to one another, albeit dual-plane viewing is thus not simultaneous; such a rotation maneuver increases the technical difficulty of ultrasound utilization. Consequently, our proposed study has the following aims and hypothesis.

1. Assess the clinical efficiency of utilization of a dual-plane simultaneous view ultrasound probe (Butterfly iQ+; Butterfly Network, Inc.) during arterial catheter placement in the operating room. Outcome metrics to include: number of attempts for successful cannulation, amount of time to complete procedure, percent of failed attempts / total attempts.
2. Assess end-user response to use of dual-plane probe via subjective feedback.

#### **II. Background and Significance**

Obtaining reliable vascular access is “one of the most basic yet critical components of patient care both in hospital and ambulatory patient settings”. Over one billion peripheral intravenous catheters (PIVCs) are placed annually worldwide, with nearly 300 million annually in the United States; this does not take into account additional vascular catheters such as central venous catheters and arterial catheters. Given that incidence it is concerning that still, first-attempt success incidence varies between 18-79%; illustrating a 21-82% first-attempt failure rate. Couple that with reported infiltration and extravasation rates of up to 69.8% related to mispositioned vascular catheters; the issue to solve is clear. Ultrasound-

[figure not shown]
guidance is a tool that increases success of accurately placed vascular catheters, yet the technology at present does not setup the end-user for as much success as possible. In providing the end-user multiple views during cannulation, the success rate and adoption of ultrasound as standard-of-practice across all vascular catheter placements is likely to increase, thereby reducing the aforementioned negative sequelae of mispositioned catheters thereby improving patient care. The patient experience is also purported to improve by reducing the number of repeated failed placement or replacement attempts, a frequently cited healthcare-fault on patient satisfaction surveys thus improving time-to-treatment and the efficiency of care.

### **III. Progress Report and Preliminary Studies**

[figure not shown]
Standard, or common, ultrasound training for vascular access utilizes a cross-sectional or short-axis view (Figure 1). Additional benefit can be gained by the end-user utilizing a longitudinal or long-axis to assist in guiding the catheter into the vessel once initial venipuncture is obtained via a cross-sectional view (Figure 2); this view, however, can be challenging to maintain intra-procedure given the narrow ultrasound array window and the narrow anatomical size of vasculature. However, current single-plane probes require the end-user to rotate the probe 90-degrees intra-procedure in order to switch between cross-sectional and longitudinal views. Therefore, the utilization of simultaneous dual-plane imaging incorporating both cross-sectional and longitudinal viewing would provide the end-user with the most comprehensive viewing strategy without necessitating manual rotation of the probe intra-procedure (Figure 3).

Overall, there is limited literature regarding bi-plane or multi-plane imaging during vascular access procedures. The literature does attest that utilization of numerous views during vascular access procedures is beneficial, yet manual rotation of the probe during cannulation is seen as a limitation. There is also support for improved success rates and less redirection with trainees when using a long-axis approach as compared to short-axis, specifically for subclavian placement. Convissar, et al (2021) describe a case study utilizing the Butterfly iQ+ for arterial line insertion with success after many failed attempts with standard ultrasound. In conclusion, it seems reasonable to use this literature as a base to do a small research study evaluating number of sticks, time to get IV, % of overall failures, etc – all the aforementioned literature is either case study or very small sample size.

In addition to the Butterfly iQ+ probe, the Phillips XL14-3 xMATRIX Linear Array Transducer is a diagnostic probe on-market capable of dual-plane viewing. The xMATRIX is limited for this application given its design for diagnostic use with extra measurement and processing functions and therefore, too high-cost and presumed low durability for point-of-care procedural applications.

[figure not shown]
[figure not shown]

(Figure 1)

(Figure 2)

### Dual-View Vascular Access Probe

(Figure 3)

## **IV. Research Design and Methods**

### **Study Design**

This investigation will employ a prospective, non-blinded randomized-control study.

Study Subjects – 50 patients who meet enrollment criteria.

Control Subjects – 50 patients who meet enrollment criteria.

Provider subjects – Up to 50 anesthesia providers (trainee, CRNA, anesthesia staff physician)

### **Inclusion criteria**

- Elective surgical patients requiring non-emergent ultrasound-guided radial arterial catheter placement
- Anesthesia providers to include trainees, certified registered nurse anesthetists (CRNA) and attending anesthesia providers.

### **Exclusion Criteria**

- Age younger than 18 years or older than 85 years.
- Pregnant
- Patients in a moribund state or palliative care only
- Vulnerable patients (i.e. Severe mental handicap, non-decisional)
- History of peripheral arterial disease
- Placement of arterial catheter without ultrasound guidance
- Provider: Medical students or CRNA students.

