## **Methods**

Anesthesia providers assigned to an upcoming rotation in the main operating rooms will receive a recruitment message via e-mail regarding participation in this study. If they consent to participate, they will be asked to view an online educational video sent to them via email (see below) and will be given an opportunity to practice use of the dual-view probe prior to use on a patient. Some providers may have utilized the dual-view technology previously.

Instructional Video for Providers: <https://www.youtube.com/watch?v=rBS3Galrqqc>

Enrolled patients will be randomized to two groups:

Protocol version v5 11022021

- Control: Arterial line placement via “standard” mechanism; utilization of a single-plane ultrasound probe
- Intervention: Arterial line placement utilizing dual-plane, Butterfly iQ+ ultrasound probe.

A Butterfly iQ+ with attached large iPAD or alternate tablet device will be utilized for this study to allow for a larger screen visualization as compared to a portable phone device.

The anesthesia provider (attending physician, CRNA, or trainee) staffed in the patient’s operating room will place the arterial line using standard practice besides randomization to the type of ultrasound probe. It will be recorded if the provider has previously utilized the dual-view probe.

The anesthesia residency program is already providing their trainees with an individual Butterfly iQ+ ultrasound probe system; therefore, these already purchased and implemented devices will be utilized in this study.

The research coordinator will utilize a stopwatch to record the amount of time required for successful placement of a peripheral arterial catheter; time recording will begin with the initial skin puncture and cease with observation of an appropriate arterial waveform on the in-room monitor.

If a patient is enrolled in the “Intervention” group and the anesthesia provider requires more than 3 attempts to achieve successful arterial catheter cannulation; the provider will discontinue use of the dual-plane probe and attempt placement with a technique of their choosing.

A picture of the ultrasound image at the completion of the procedure, successful or unsuccessful, will be obtained; no patient-specific information will be recorded.

All data will be collected, organized, and analyzed with the aid of a dedicated biostatistician from the Health Science Research office. Estimate for their work are included in the attached budget.

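### Does the exclusion for catheters placed without ultrasound let dual-plane failures be dropped after randomisation?

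*Protocol*

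**What the plan says.** Entry is limited to "Elective surgical patients requiring non-emergent ultrasound-guided radial arterial catheter placement" (Protocol, Inclusion criteria). The Exclusion Criteria add the bullet "Placement of arterial catheter without ultrasound guidance", with no time point and no word such as planned.

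The Study Design section describes a "prospective, non-blinded randomized-control study" with 50 patients per group, each group defined as patients meeting the enrolment criteria. Methods then states "Enrolled patients will be randomized to two groups". The control arm is described as "Control: Arterial line placement via “standard” mechanism; utilization of a single-plane ultrasound probe". A switching rule is written for one arm only: "If a patient is enrolled in the “Intervention” group and the anesthesia provider requires more than 3 attempts to achieve successful arterial catheter cannulation", then "the provider will discontinue use of the dual-plane probe and attempt placement with a technique of their choosing".

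The primary outcome is first-stick success, and the Secondary Outcomes section defines an attempt as one needle insertion through the skin. The SAP is a short paragraph that labels the analysis exploratory. It names no analysis set and gives no rule for rescued patients.

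**The concern.** The inclusion criterion already requires ultrasound-guided placement, so at screening the exclusion bullet seems to add nothing. That invites the reading that it refers to how the catheter was finally placed, which is known only after randomisation. The rescue rule then supplies a route: a dual-plane patient who has failed repeatedly may be cannulated without ultrasound and so literally meet the bullet.

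The direction of any resulting bias would be fixed. Anyone who reaches the rescue rule has already failed at the first stick, so removing that patient can only raise the dual-plane success rate. The written route exists only in the intervention arm, the trial is open-label, and no stated analysis population stands in the way. At stake would be a false advantage for the dual-plane probe on the primary outcome, and similarly on number of attempts and time.

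**Working it through.** **Step 1: when the criterion is judged.** Three places in the Protocol bear on this.

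- Study Design counts patients who meet the enrolment criteria.
- Methods randomises patients who are already enrolled.
- Every other patient bullet under Exclusion Criteria (age, pregnancy, moribund or palliative status, vulnerability, peripheral arterial disease) is known at baseline.

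The sequence is criteria, enrolment, randomisation, placement. Whether the team intends to use ultrasound is known at the first step. The bullet fits as the negative form of the inclusion criterion. Redundant drafting of that kind is common and is not evidence of a second, post-randomisation rule.

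**Step 2: when the primary outcome is fixed.** First-stick success is decided at the first needle insertion, which in both arms is made with the assigned ultrasound probe. The rescue rule operates only after more than three insertions. A rescued patient therefore has a complete primary outcome, a failure, before the technique changes.

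**Step 3: what the documents do with failures.** Methods asks for an image at the end of the procedure whether or not it succeeded. Secondary Outcomes and Data Collection both include failed attempts that end in unsuccessful cannulation. No passage removes a rescued patient.

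**Step 4: size if such patients were removed anyway.** Inputs: 50 per arm (Study Design). Assumptions, because the documents give no values:

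- the true per-attempt success probability *p* is the same in both arms;
- attempts are independent;
- a fraction *f* of the patients who fail three attempts are rescued without ultrasound and dropped;
- no control patient is dropped.

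Expected number past three attempts = 50(1 − p)³. Apparent first-stick rate = p / [1 − f(1 − p)³].

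- p = 0.5: 50 × 0.125 = 6.25 patients. With f = 1, 0.5/0.875 = 57.1%, a gain of 7.1 points. With f = 0.5, 0.5/0.9375 = 53.3%, a gain of 3.3.
- p = 0.6: 50 × 0.064 = 3.2 patients. With f = 1, 0.6/0.936 = 64.1%, a gain of 4.1. With f = 0.5, 0.6/0.968 = 62.0%, a gain of 2.0.
- p = 0.7: 50 × 0.027 = 1.35 patients. With f = 1, 0.7/0.973 = 71.9%, a gain of 1.9. With f = 0.5, 0.7/0.9865 = 71.0%, a gain of 1.0.
- p = 0.4, f = 1: 0.4/(1 − 0.216) = 51.0%, a gain of 11.0.

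If more than three attempts means that the switch follows a fourth failure, the exponent becomes 4. The f = 1 gains for p = 0.5, 0.6 and 0.7 then fall to 3.3, 1.6 and 0.6 points.

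**Step 5: effect on the error rate.** Exact binomial enumeration of a pooled two-proportion z-test, two-sided 0.05, with the switch after three failures:

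| p | nobody dropped | f = 0.5 | f = 1 |
|---|---|---|---|
| 0.5 | 0.057 | 0.063 | 0.107 |
| 0.6 | 0.052 | 0.056 | 0.071 |
| 0.7 | 0.050 | 0.052 | 0.056 |

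The column for nobody dropped corresponds to the plan as written.

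**The case for a change.** The best case for changing the plan is that one bullet admits two readings with different primary denominators, and the choice between them could be made with arm and outcome known. An analyst who took the literal reading would break no written rule, since neither document commits to analysis by assigned arm. The remedy would also be cheap: one reworded bullet and one SAP sentence.

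Part of this stands. The bullet does lack the word planned, the analysis population is unstated, and the arithmetic in the working is correct. At *p* = 0.5 with every such patient dropped, the type I error roughly doubles.

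The step from open wording to bias is the weak part. It needs four things in sequence: more than three attempts; a choice to abandon ultrasound altogether, because a switch to a single-plane probe would not meet the bullet; a literal, post-randomisation reading of an eligibility criterion; and a decision to discard a patient whose primary outcome is already recorded. The last two have no support in the text beyond not being forbidden.

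The asymmetry between arms is also less firm than it looks. Providers otherwise follow standard practice, and nothing stops a control provider from changing technique after repeated failures. Under the literal reading those control failures would be dropped too, which would offset some of the inflation. The calculation sets that number to zero.

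One argument for leaving the plan alone deserves little weight. The Data Collection list has no item for the final technique, so nothing planned would identify these patients. But that list also omits the randomised arm, so it is plainly not exhaustive.

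**Conclusion.** No change follows. Applied in the order the Protocol gives, eligibility is settled before randomisation and a rescued dual-plane patient stays in the data as a first-stick failure. The bias on the primary comparison is then zero. The inflation of about 2 to 7 points for *p* from 0.7 down to 0.5 (11 points at *p* = 0.4) is a ceiling. It assumes equal arms, independent attempts, a switch after exactly three failures, every rescue done without ultrasound, every such patient removed and no control patient removed. With half removed, the range for *p* from 0.7 to 0.5 is 1.0 to 3.3 points.

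What remains is missing detail: the criterion does not say that it means planned technique, and a brief SAP does not name its analysis set. Analysing randomised patients in their assigned arm is the ordinary way for a trial statistician to fill that gap, and nothing in either document points elsewhere. The conclusion would change only if a document, or the reported patient flow, showed rescued patients being excluded after randomisation.

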## **Methods**

Anesthesia providers assigned to an upcoming rotation in the main operating rooms will receive a recruitment message via e-mail regarding participation in this study. If they consent to participate, they will be asked to view an online educational video sent to them via email (see below) and will be given an opportunity to practice use of the dual-view probe prior to use on a patient. Some providers may have utilized the dual-view technology previously.

Instructional Video for Providers: <https://www.youtube.com/watch?v=rBS3Galrqqc>

Enrolled patients will be randomized to two groups:

Protocol version v5 11022021

- Control: Arterial line placement via “standard” mechanism; utilization of a single-plane ultrasound probe
- Intervention: Arterial line placement utilizing dual-plane, Butterfly iQ+ ultrasound probe.

A Butterfly iQ+ with attached large iPAD or alternate tablet device will be utilized for this study to allow for a larger screen visualization as compared to a portable phone device.

The anesthesia provider (attending physician, CRNA, or trainee) staffed in the patient’s operating room will place the arterial line using standard practice besides randomization to the type of ultrasound probe. It will be recorded if the provider has previously utilized the dual-view probe.

The anesthesia residency program is already providing their trainees with an individual Butterfly iQ+ ultrasound probe system; therefore, these already purchased and implemented devices will be utilized in this study.

The research coordinator will utilize a stopwatch to record the amount of time required for successful placement of a peripheral arterial catheter; time recording will begin with the initial skin puncture and cease with observation of an appropriate arterial waveform on the in-room monitor.

If a patient is enrolled in the “Intervention” group and the anesthesia provider requires more than 3 attempts to achieve successful arterial catheter cannulation; the provider will discontinue use of the dual-plane probe and attempt placement with a technique of their choosing.

A picture of the ultrasound image at the completion of the procedure, successful or unsuccessful, will be obtained; no patient-specific information will be recorded.

All data will be collected, organized, and analyzed with the aid of a dedicated biostatistician from the Health Science Research office. Estimate for their work are included in the attached budget.

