## **Endpoints**

Successful placement of peripheral radial arterial catheter as evidenced by transduction of arterial waveform on bedside monitor.

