## **Secondary Outcomes**

- Number of attempts to achieve successful arterial catheter cannulation; “attempt” will be defined as a single insertion of the needle into the skin.
- Amount of time required for successful arterial catheter cannulation.
- Number of failed attempts leading to unsuccessful arterial catheter cannulation
- Subjective response from anesthesia provider regarding their experience utilizing a single-plane versus a dual-plane ultrasound probe.
  - Please explain your experience using this ultrasound probe.
  - If you used the dual-view probe, how do you feel that this dual-view probe impacted your procedure as compared to a single-view ultrasound probe?

- Do you feel that the dual-view ultrasound probe provides a procedural benefit over the single-view ultrasound probe; please explain.

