### **Subject Safety**

Enrolled patients will be exposed to minimal additional risk. The additional risk may include additional peripheral arterial catheter placement attempts which may lead to hematoma formation, bleeding, artery injury, and necessitation to identify alternative anatomic sites for successful arterial catheter placement.

There will be no additional risk posed to the anesthesia providers.

Given the fact that this is considered a low-risk intervention, we will apply for a waiver of documentation of informed consent from the patient and anesthesia provider.

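### Time and attempts are defined only up to a successful cannulation, and no rule keeps never-cannulated patients in the regression, while a change of technique is prescribed in one arm only (secondary outcomes)

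*Protocol*

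**What the plan says.** **Outcomes.** The Protocol's Secondary Outcomes list time as "Amount of time required for successful arterial catheter cannulation" and define the attempts outcome in the same way, as the count up to success. In Methods the stopwatch has one stopping point: "time recording will begin with the initial skin puncture and cease with observation of an appropriate arterial waveform on the in-room monitor". Endpoints defines success as "Successful placement of peripheral radial arterial catheter as evidenced by transduction of arterial waveform on bedside monitor".

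**Failures are foreseen.** Methods says: "A picture of the ultrasound image at the completion of the procedure, successful or unsuccessful, will be obtained". Secondary Outcomes, and again Data Collection, list a separate item: "Number of failed attempts leading to unsuccessful arterial catheter cannulation".

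**Change of technique.** Methods provides that, in the intervention group, once more than 3 attempts are needed, "the provider will discontinue use of the dual-plane probe and attempt placement with a technique of their choosing". For control it names a single-plane probe and standard practice, with no stated point of change. Exclusion Criteria lists "Placement of arterial catheter without ultrasound guidance".

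**Analysis.** The SAP gives log transformation and linear regression at a two-sided 0.05 level and calls the analysis exploratory. It does not name the outcomes modelled. It gives no analysis set and no rule for unsuccessful procedures, censoring or patients who changed technique.

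**The concern.** Whether a patient is ever cannulated is settled after randomisation and may depend on the arm. A regression of log time or log attempts-to-success can use only patients who have a value, so it compares those who succeeded. If the shares of failures are equal, little is lost. If they differ, the arm that leaves more hard cases without a catheter loses those cases from its average and looks more efficient.

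The one-sided change rule is a concrete reason why the shares could differ. From the fourth insertion on, intervention patients may receive something other than the dual-plane probe, while control continues as before. Time and attempts are efficiency measures named in the first Specific Aim, so a result in the wrong direction would bear on what the trial reports about the probe.

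**Working it through.** The plan gives no power, success rate or failure rate for these outcomes, so there is no figure of its own to reproduce. What follows is an illustration.

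**Inputs from the documents:** 50 per arm (Study Design); change of technique after more than 3 attempts, intervention only (Methods); two-sided 0.05 (SAP).

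**Assumptions:** each insertion succeeds independently with probability p in both arms for the first 3 insertions. From the fourth insertion, success is p2 in intervention and stays p in control. Both arms stop at 5 insertions. The first-attempt rates in the Protocol's Abstract concern peripheral intravenous catheters, so p is varied.

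**Formulas,** with q = 1 − p (for control, p2 = p):
- Never cannulated = 50 × q³ × (1 − p2)².
- Probability that insertions 1 to 5 are the successful one: p, qp, q²p, q³p2, q³(1 − p2)p2.
- Mean attempts among successes = Σ k·P(k) / Σ P(k).

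**At p = 0.4:**
- Control: never cannulated 50 × 0.6⁵ = 3.9. Mean = (0.4 + 0.48 + 0.432 + 0.3456 + 0.2592) / 0.92224 = 1.9168 / 0.92224 = 2.08.
- Intervention, p2 = 0.2: never cannulated 50 × 0.216 × 0.64 = 6.9. Mean = (1.312 + 0.1728 + 0.1728) / 0.86176 = 1.6576 / 0.86176 = 1.92.
- Intervention, p2 = 0.6: never cannulated 50 × 0.216 × 0.16 = 1.7. Mean = (1.312 + 0.5184 + 0.2592) / 0.96544 = 2.0896 / 0.96544 = 2.16.

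Both comparisons point the wrong way. The arm with more failures shows fewer attempts, and the arm with fewer failures shows more.

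**Same formulas at higher p, with p2 = p − 0.2:**

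| p | Never cannulated, intervention vs control | Mean attempts among successes, intervention vs control |
|---|---|---|
| 0.4 | 6.9 vs 3.9 | 1.92 vs 2.08 |
| 0.5 | 3.1 vs 1.6 | 1.76 vs 1.84 |
| 0.6 | 1.2 vs 0.5 | 1.58 vs 1.61 |
| 0.7 | 0.3 vs 0.1 | 1.41 vs 1.42 |

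**Power of the alternatives,** by simulation. The setting is a stop at 5 with success after the change as in control; each insertion takes a lognormal time (median 60 s, log-SD 0.5, both assumed). The Monte Carlo standard error is at most 0.9 points.

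| p, control vs intervention | Attempts: successes only / worst rank | Time: successes only / worst rank / cumulative incidence |
|---|---|---|
| 0.4 vs 0.6 | 59% / 69% | 42% / 53% / 62% |
| 0.5 vs 0.7 | 62% / 65% | 41% / 45% / 57% |
| 0.6 vs 0.8 | 67% / 65% | 39% / 37% / 50% |

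Successes only is a t-test on the log scale. Worst rank is a Mann-Whitney test with failures tied last. Cumulative incidence is a log-rank test with failures held in the risk set to the end. If success after the change is 0.2 below control, the gain for attempts vanishes (67% versus 67% at 0.4 versus 0.6).

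**The case against.** The strongest case against is that the reversal sits in a corner. It needs low per-attempt success, a later technique that works clearly better or worse, and a stopping point that the plan does not state. Where success after the change equals p, the successes-only test rejects about 5% of the time. The outcomes are secondary and the SAP calls the analysis exploratory. All of this stands, and it limits the size of the point. It does not remove the gap: a patient without a waveform still has no defined time.

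Four stronger readings are tempting, and the documents do not support them.
- *That these patients have no attempts data.* Their failed attempts are on the data collection list. What is missing is a rule that joins that count to attempts-to-success.
- *That the plan drops them.* The SAP states no complete-case rule. Their loss is an inference from how such a regression is ordinarily fitted.
- *That patients who change to a technique without ultrasound are removed after randomisation.* The no-ultrasound item stands in an eligibility list, and no text applies it after the change.
- *That the type I error is inflated.* If later success differs between arms, the randomised strategies truly differ, so rejections are partly real. The error is one of direction.

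Two apparent conflicts are weak. Subject Safety mentions "necessitation to identify alternative anatomic sites for successful arterial catheter placement" as a possible harm and does not define success. The Specific Aims describe time loosely, while Methods and Secondary Outcomes carry the operative definition.

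**Conclusion.** The point holds as a cheap improvement to the secondary efficiency outcomes. Followed as written, the plan conditions time and attempts on a success that occurs after randomisation, with a change of technique prescribed in one arm only. A comparison of successes can then favour the arm with more failures.

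In the illustration at p = 0.4 the apparent advantage is 2.08 − 1.92 = 0.16 attempts, against 6.9 − 3.9 = 3.0 more patients without a catheter. At p = 0.7 or more the effect is negligible. These sizes rest on the assumed success rates, the assumed stop at 5 and independent insertions. The primary outcome, first-stick success, is not affected, because it is known after the first insertion and precedes any change.

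**What to change.** Add to the SAP, for the secondary outcomes:

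1. Time and attempts are analysed for all randomised patients in their assigned arm, counted to waveform whatever technique is used later. No randomised patient is removed for that technique.
2. Time: cumulative incidence of cannulation, with never-cannulated patients kept in the risk set to the end. Worst rank serves as a sensitivity analysis.
3. Attempts: a rank comparison with never-cannulated patients tied at the worst rank.
4. The number never cannulated is reported per arm.

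Separately, the investigators should reconcile the one-arm change rule in Methods with the control procedure and with the no-ultrasound item in Exclusion Criteria. No clinical rule is proposed here.

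**Cost.** A few sentences and no new data field, since unsuccessful cannulation is already recorded. This remains possible although the SAP, dated September 1, 2023, describes the analyses in the past tense; in that case the analyses should be labelled as added later. Time would no longer be reported as a mean. If everyone is finally cannulated, ranking attempts costs about 2 to 5 points of power against the log regression (69% versus 71% at 0.4 versus 0.6; 64% versus 69% at 0.5 versus 0.7; 65% versus 70% at 0.6 versus 0.8).
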